6.3 Treatment of missing data for primary study outcomes

For cohort 1 and 3, we will conduct multiple imputation of missing longitudinal anthropometric data using chained regressions (Stata: `mi impute chained (regress)`) which imputes missing values under the missing at random assumption⁶. Imputation variables will be the wide-form anthropometric measurements and child age, and complete predictors (independent variables) will be child sex and randomization stratum. We will use 50 imputations (Stata: `add`) with 10 iterations within imputation (Stata: `burnin`) to allow for convergence to a stationary distribution before the imputation. We will inspect imputation quality using trace plots by iteration to assess convergence and box plots to compare distributions of observed and imputed values. In addition, we will examine the fit of imputed child length values along the growth curves.

6.4 Impact assessments

6.4.1 Main analyses

Impact on wasting longitudinal prevalence (primary outcome of cohort 1), wasting incidence (primary outcome of cohort 3), MAM and SAM longitudinal prevalence and incidence, and morbidity longitudinal prevalence, will be estimated using a mixed effects Poisson regression model with robust estimation of standard errors.

For other longitudinal outcomes, we will use linear mixed-effects regression models to assess the impact of the intervention on continuous outcomes and linear probability mixed-effects regression models with robust estimation of standard errors to assess the impact of the intervention on binary outcomes (19). Repeated visits within a child in longitudinal models will be accounted for by including a random intercept at the child level and a random slope at the visit level (defined as number of months since enrollment). For longitudinal models with continuous anthropometric outcomes (growth curves analyses), we will assess if the addition of a quadratic term of time (visit) improves the model fit significantly by applying a likelihood ratio test comparing the model with and without the quadratic term. To assess the specific

⁶ De Silva AP, Moreno-Betancur M, De Livera AM, Lee KJ, Simpson JA. (2017) A comparison of multiple imputation methods for handling missing values in longitudinal data in the presence of a time-varying covariate with a non-linear association with time: A simulation study. *BMC Med Res Methodol*; 17:1–11

impact of the intervention from enrollment at the age of 6 months to the end of follow-up, we will assess the interaction between intervention allocation and time (visit).

For cross-sectional analyses on outcomes measured at exit from cohorts 1 and 3 (mainly cumulative outcomes such as knowledge, vaccination, stunting, etc...) and on cohort 2 outcomes, we will use linear probability mixed-effects regression models with robust estimation of standard errors to assess the impact of the intervention on binary outcomes (including recovery rate, primary outcome of cohort 2), and linear mixed-effects regression models to assess impacts on continuous outcomes (19).

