3.4.2 Secondary study outcomes

Secondary outcomes of the study include:

For Cohorts 1 and 3 :

- The longitudinal prevalence of :
 - Wasting, defined as above (cohort 3)
 - MAM, defined for each child as the number of MAM diagnoses divided by the total number of monthly visits made
 - SAM, defined for each child as the number of SAM diagnoses divided by the total number of monthly visits made
- The incidence of :
 - Wasting, defined as above (cohort 1).
 - MAM, defined as the number of new MAM cases recorded during monthly visits.
 - SAM, defined as the number of new SAM cases recorded during monthly visits.
- The prevalence of anemia defined as the proportion of children with a hemoglobin level below 11g/dl at the end of the study.
- Mean hemoglobin concentration at the end of the study.
- Prevalence of stunting defined as the proportion of children with HAZ <-2 (relative to the 2006 WHO reference) at the end of the study.
- The average z-scores HAZ at the end of the study.
- Wasting screening coverage defined as the proportion of children screened (using MUAC, weight-for-height or bilateral edema) in the month prior to the monthly visit. Two sub-outcomes will also be considered:
 - Screening coverage by care groups.
 - Screening coverage of the family MUAC component, which is the screening performed by a family member in the past month.
- Linear growth rate defined as the change in height-for-age index per month.
- Speed of weight growth defined as the change in weight-for-height index per month.
- Weight gain defined as the weight change per month.
- MUAC gain defined as the change in MUAC per month.

- The longitudinal prevalence of childhood morbidity, i.e. acute respiratory infections, fever, diarrhea and malaria, defined as the number of reports of signs of these morbidities divided by the total number of days reported (1-3 per monthly visit made).
- Mother/guardian's knowledge of nutrition, WASH, and health expressed as cumulative total and domain scores at exit.
- Infant and young child feeding (IYCF) practices:
 - Introduction of (semi) solid and soft complementary foods .
 - Minimum dietary diversity in children, defined as the proportion of children who consumed at least 5 of the 8 food groups (including breast milk) the day before the survey.

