3.5 Sample Size

3.5.1 Cohort 1 – primary outcome: longitudinal prevalence of wasting

The main cohort (#1) will include 1,750 children in the community aged 6 to 6.9 months, included for a period of 7 months and followed up monthly until the end of the study (total duration: 9 months).

The main cohort (#1) will include children aged 6-6.9 months. Given the small size of most villages and the sample size needed to detect a significant, plausible and meaningful difference in longitudinal wasting prevalence (primary outcome) between groups, we have calculated that we need to include an average of 3 children per month for 7 months in the 50 largest villages (25 villages in the control group and 25 in the intervention group) and an average of 2 children per month for 7 months in the 50 smallest villages in the study area (i.e., the medium-sized villages in the Mongo Health District: equally 25 in the control group and 25 in the intervention group). The children will all leave the cohort in the same month: counting the month of inclusion, the children will be seen for a maximum of 9 months (for children included at the start of the study) and a minimum of 3 months (for children included during the 7th month). This will result in a total sample of 1,750 children (10,500 visits in total of which 1,750 inclusions and 8,750 follow-ups). With 15% dropout, **the size of this study would provide sufficient power to detect a relative decrease of about 35% in the longitudinal prevalence of wasting**, with a power of 80% and a statistical significance of 5%, taking into account the cluster effect at the village level and the imbalance in cluster size.

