6.1 Guiding principles and analysis strategy

Data will be analyzed on intent-to-treat basis. To allow for an analysis “as randomized” in the presence of missing data, we will impute missing data of the primary outcomes of the longitudinal study using a multiple imputation strategy under the *missing at random* assumption (see section 6.3 below). Data management, data cleaning, and statistical analyses will be done using Stata 17.0 (Statacorp, USA). The statistical significance will be set at 5%. All statistical tests will be two-sided. The analysis of primary study outcomes will not be adjusted for multiple testing (n=3 primary study outcomes) given the data involved represent three distinct experimental and control study samples with each one primary study outcome.

We will present results from non-adjusted and adjusted linear mixed effects regression models.

The non-adjusted models to analyze cohort 1 and 3 data will use *village (cluster)* as a random intercept and sampling stratum as a fixed effect to represent the study design. The non-adjusted models to analyze cohort 2 data will include sampling stratum as a fixed effect and will use a random intercept at the health center level and a random slope at the village level, to account for nesting of villages (clusters) into health centers (where treatment occurs for children from several villages).

In addition, we will conduct adjusted analyses, adjusting for the following variables:

- covariates that appear imbalanced at enrollment (absolute difference >10 pp) and are unlikely to have been impacted by exposure to the intervention before 6 months of age (cohort 1 and 3; virtually no household, parental or sociodemographic child level data collected at admission in cohort 2).
- child sex, and whether child was the first live birth, since a recent meta-analysis has reported that imbalance in child nutritional status between study groups can be associated to the imbalance in child sex and primiparity (3) (all adjusted models, except that data on first live birth are missing for cohort 2).
- month of enrollment (longitudinal models, cohorts 1 and 3) or month of admission into treatment (cohort 2).
- Child age at enrollment (cohort 3; constant in cohort 1; not detailed in MAM treatment registers used for cohort 2).
- type of nutrition unit where the child is/was treated (cohorts 2 and 3).

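### The arm-by-visit test of growth in cohorts 1 and 3 has no village-level slope and no stated robust standard errors, so it rejects more often than 5% whenever villages differ in growth rate

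*SAP*

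**What the plan says.** SAP 6.1 gives the non-adjusted models for cohorts 1 and 3 the village "as a random intercept and sampling stratum as a fixed effect to represent the study design". SAP 6.4.1 then deals with repeated visits within a child by "including a random intercept at the child level and a random slope at the visit level", where visit is counted in months since enrollment. For the effect between age 6 months and the end of follow-up, it states that "we will assess the interaction between intervention allocation and time (visit").

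On variance estimation, SAP 6.4.1 names robust standard errors for the Poisson models. For the other longitudinal outcomes it specifies "linear mixed-effects regression models to assess the impact of the intervention on continuous outcomes and linear probability mixed-effects regression models with robust estimation of standard" … In that sentence the robust errors belong to the linear probability models for binary outcomes. The later paragraph on cross-sectional outcomes draws the same distinction. The only random slope placed at village level is in the cohort 2 model (SAP 6.1).

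SAP 3.4.2 lists four per-month growth measures among the secondary outcomes of cohorts 1 and 3, for example "Linear growth rate defined as the change in height-for-age index per month". The error rate is general: "The statistical significance will be set at 5" percent, and "All statistical tests will be two-sided" (SAP 6.1).

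**The concern.** Arm is allocated by village, so the arm-by-visit coefficient compares village growth slopes between arms. A village random intercept absorbs village differences in level but not in slope. With slopes random only at child level, the model treats the slopes of children in the same village as independent given arm. Its implied null is then that the arms do not differ and that villages do not differ in growth either. The question asked concerns only the first part.

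The documents make village differences in growth credible. They describe seasonal food insecurity and limited access to clean water (Protocol 3.1.1), product shortages that were uneven across facilities (a third of 18 had five or more in 24 months), and earlier care groups or family MUAC training in some comparison areas (SAP Table 1).

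At stake are the confidence intervals and tests for growth in continuous secondary outcomes. The pooled analysis in SAP 6.4.3 would bring about (1,750 + 700)/100 = 24.5 children per village into the same structure. The effect-modification models in SAP 6.4.4 reuse the earlier models.

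**Working it through.** **Inputs from the documents**
- 100 villages, 50 per arm; two-sided 5% test.
- Cohort 1: 50 × 21 + 50 × 14 = 1,750 children. Monthly intakes of 250 are seen 9, 8, …, 3 times: 250 × (9+8+7+6+5+4+3) = 10,500 visits. Both totals match SAP 3.5.1.
- Cohort 3: 50 × 8 + 50 × 6 = 700 children; 700 × 7 = 4,900 visits. Both match SAP 3.5.3.

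**Inputs assumed (not in the documents)**
- Weight-for-height-like values: child intercept SD 0.9, village intercept SD 0.2, residual SD 0.35, slope SD 0.05, 0.08 or 0.12 per month.
- Share ρ of slope variance lying between villages: 0 to 20%. The only intra-cluster coefficient in the documents, 0.05, is for recovery in cohort 2 and says nothing about growth slopes.

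**Method**
1. Fixed effects: intercept, visit, arm, size stratum, arm × visit. V_m is the covariance under the SAP model (village intercept, child intercept and slope). V_t is the same, except that a share ρ of the slope variance is moved to village level.
2. Model-based variance: A⁻¹ with A = ΣX′V_m⁻¹X. True variance of the same estimator: A⁻¹BA⁻¹ with B = ΣX′V_m⁻¹V_tV_m⁻¹X. Sums run over villages.
3. R = true variance / model-based variance for arm × visit.
4. Actual error = 2 × [1 − Φ(1.96/√R)].

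**Stated figure first.** At ρ = 0, R = 1.00 and the error is 5.0%, as the SAP intends.

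**Cohort 1, slope SD 0.08**
- ρ = 5%: R = 1.383; 1.96/√1.383 = 1.667; error 9.6%.
- ρ = 10%: R = 1.765; 1.96/√1.765 = 1.475; error 14.0%. The reported standard error is 1/√1.765 = 0.75 of the true one, about 25% too small.
- ρ = 20%: R = 2.531; 1.96/√2.531 = 1.232; error 21.8%.

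**All scenarios: actual error (%) at slope SD 0.05 / 0.08 / 0.12**

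| Village share of slope variance | Cohort 1 | Cohort 3 |
|---|---|---|
| 0 | 5.0 / 5.0 / 5.0 | 5.0 / 5.0 / 5.0 |
| 2% | 6.1 / 6.8 / 7.4 | 5.5 / 5.8 / 6.1 |
| 5% | 7.8 / 9.6 / 11.2 | 6.3 / 7.1 / 7.8 |
| 10% | 10.5 / 14.0 / 17.0 | 7.6 / 9.3 / 10.6 |
| 20% | 15.9 / 21.8 / 26.3 | 10.3 / 13.6 / 16.0 |

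Cohort 3 is milder because it has about 7 children per village against 17.5 in cohort 1.

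**Simulation, cohort 1 (400 trials per cell, no arm effect)**
- Slope SD 0.08, SAP model: 6.8%, 9.8%, 14.0% and 23.8% at shares of 0, 5%, 10% and 20%. At 5%, 10% and 20%, adding a village slope gave 5.5%, 6.5% and 6.3%; village-robust errors gave 5.5%, 6.0% and 5.5%.
- Slope SD 0.10 with a smaller residual SD of 0.2, SAP model: 4.3%, 11.5% and 20.5% at shares of 0, 5% and 10%. With a village slope the error was 4.25% at both 5% and 10%.

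Monte Carlo standard errors are about 1 to 2 points. The inflated cohort 3 figures are analytic only.

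**The case against.** **The size rests on an undocumented input.** This stands. At a 2% share, cohort 1 error is only 6-7%. A reader might infer that false growth claims will occur at two to four times the nominal rate, or that one range such as 10-22% covers both cohorts. The documents support neither: they give no village slope variance, and cohort 3 falls well below cohort 1 under the same assumptions.

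**The modelled schedule has been superseded.** This also stands. SAP Table 2 lengthens cohort 1 by a month and splits exits over the last two months. In cohort 3 it lifts the per-village cap and shortens some follow-up. The planned 15% dropout is not modelled either. In the simple approximation R = 1 + (m − 1)ρ, dropout takes m from 17.5 to 14.9 and the error at ρ = 5% from 14.7% to 13.2%. That formula runs higher than the table because it ignores the noise in each child's estimated slope. The schedule changes may pull either way; none removes the mechanism.

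**The per-month changes might themselves be the dependent variable.** SAP 3.4.2 would allow this. The village intercept would then absorb clustering in growth rate. So it is not certain that the interaction decides all four growth-rate outcomes. SAP 6.4.1 still states the interaction as the test of impact from 6 months onward, and the point applies to that test.

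**The omission may be loose drafting.** The slope wording names the visit rather than a grouping unit, and SAP 6.2.1 does apply robust errors to continuous outcomes, though only for cohort 3 enrollment comparisons. But the sentence in 6.4.1 concerns visits within a child, and the contrast between continuous and binary models is drawn twice there. An analyst following the text would fit the model examined here.

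**Conclusion.** The point holds for the arm-by-visit interaction in longitudinal linear models of continuous outcomes in cohorts 1 and 3. As written, that test ignores village variation in slope, so its standard error is too small whenever such variation exists. The structural conclusion follows from the text. The size is conditional on an assumed village share of slope variance, the assumed variance components and the originally planned schedule. It runs from 5% with no village variation to the 20% row of the table.

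A reader might extend this to the trial's main results; the documents do not support that. The Poisson primary outcomes of cohorts 1 and 3, recovery in cohort 2 and the binary outcomes all have robust standard errors stated. The plan should be changed, but no primary conclusion depends on it.

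**What to change.** In SAP 6.4.1, for longitudinal models of continuous outcomes in cohorts 1 and 3, and for the pooled analysis in 6.4.3, add a village-level random slope on visit alongside the village intercept (Stata: `|| village: visit || child: visit`). If that model does not converge, use robust standard errors clustered on village. Name the clustering level, since the SAP elsewhere says only that estimation is robust. Base the arm-by-visit test and its confidence interval on that model. The same sentence should say that the existing visit slope is at child level, and whether the per-month growth outcomes are analysed through this interaction.

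The cost is a sentence or two in the SAP and one term or option in the code, with no new data. Intervals will be somewhat wider when villages truly differ in slope, and some models may need convergence work.

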6.4.2 Sub-group analyses

For cohort 1 and 3 data, we will conduct exploratory subgroup analysis of treatment coverage on the sub-group of children with wasting and children recovering from wasting.

For cohort 2 data, we will conduct exploratory subgroup analyses by type of treatment unit, because two distinct treatment protocols are used in Chad for SAM and MAM, and within MAM treatment, implementation strategies are different between the health center platform and the community platform, including the use of two distinct treatment products. These analyses may help explain wasting treatment outcome results.

6.4.3 Sensitivity analyses

We will assess whether impacts on primary outcomes in cohort 1 and 3 are sensitive to the definition of wasting, by assessing impact on wasting prevalence and incidence when wasting is defined with 2 alternative definitions: 1) MUAC < 125 mm or oedema, and 2) WLZ < -2 Z-scores or oedema.

The data from cohort 1 and 3 will be pooled to assess the impact of the intervention on the longitudinal prevalence and secondary study outcomes and incidence of wasting with a larger statistical power. The cohort will be considered a strata and added in all models as a fixed effect.

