While the main cohort study is an experimental study³, the treatment cohort and relapse prevention study are quasi-experimental in nature. The quasi-experimental character of these two sub-studies implies the random character of the intervention and comparison group is not fully guaranteed. More precisely, children enrolled in the treatment cohort may not be comparable between study groups because the BCC and food supplement may prevent a proportion of the usual prevalence of wasting. Similarly, a higher screening coverage or screening by family MUAC may refer children with wasting with different characteristics as compared to those in the comparison group. Therefore, any impact or lack of impact of the intervention to support the CMAM services need to be interpreted with caution, as it may be a result of both the intervention and any different characteristics of the enrolled samples of children. For the same reasons, the results of the relapse prevention study must be interpreted bearing in mind possible impacts of the preceding preventive BCC and food supplement and improved screening and referral (studied in the main cohort), as well as possible impacts on the adherence and recovery rates of CMAM services (studied in the treatment cohort).

³ The main cohort study is an experimental cluster-randomized controlled study that guarantees (if random allocation of clusters is successful) that the samples of children enrolled in the intervention and comparison group have similar household, caregiver, and child characteristics. Therefore, any observed impacts can be exclusively associated with the intervention.

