3.5.3 Cohort 3 - Primary Outcome: incidence of relapse

The relapse prevention cohort (#3) will include 700 [6-23] months old children living in the 100 villages in the study area, who were discharged from treatment and recovered from wasting, and will be followed up monthly for 6 months.

Given the small size of most villages and the required sample size, we have calculated that we need to enroll 8 children in the 50 largest villages and 6 children in the 50 average villages and follow them every month for 6 months each. This will result in a total sample size of 700 children (4,900 visits in total, including 700 inclusions and 4,200 follow-ups). **Such a sample size would provide sufficient power to detect a decrease of about 33% in the incidence of relapse.**

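### The pooled cohort 1 and 3 analysis mixes a randomised sample with one selected after randomisation, so it cannot be read as the randomised effect

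*SAP*

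**What the plan says.** SAP section 6.4.3 (Sensitivity analyses) states: "The data from cohort 1 and 3 will be pooled to assess the impact of the intervention on the longitudinal prevalence", and extends this to the secondary outcomes and the "incidence of wasting with a larger statistical power". The only provision made for combining the two samples is this: "The cohort will be considered a strata and added in all models as a fixed effect". The section has no arm-by-cohort term, no rule for a child who belongs to both cohorts, and no caution about interpretation.

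SAP section 3.2 separates the two designs. It opens "While the main cohort study is an experimental study" and continues that "the treatment cohort and relapse prevention study are quasi-experimental in nature", so that "the random character of the intervention and comparison group is not fully guaranteed". It asks that relapse results be read with the possible earlier effects of prevention, screening and treatment in mind. For the same reason, section 6.2.1 plans to test baseline differences between arms in cohort 3 but not in cohort 1.

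**The concern.** Cohort 1 is a random sample of six-month-olds in randomised villages. Cohort 3 consists of children who became wasted, were treated and recovered, and each of those steps can be influenced by the intervention. A cohort fixed effect absorbs a difference in the average level of wasting between the samples. It cannot absorb a difference between arms in who reaches cohort 3.

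The pooled model also assumes one arm effect, although the packages differ. SAP Table 1 lists separate prevention and relapse-prevention components, with different age ranges and inputs. For incidence, the pooled outcome combines wasting in community children with relapse in recovered children.

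A sensitivity analysis normally asks whether a result survives a change of assumptions about the same quantity. This one changes the quantity, and its stated aim is power. What is at stake is interpretation: a null cohort 1 result could stand beside a significant pooled result that appears to support the intervention but is driven by cohort 3.

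A smaller issue is that nothing prevents a child from contributing the same calendar months through both cohorts.

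**Working it through.** **1. Planned sizes (SAP 3.5.1 and 3.5.3; protocol Table 1).**
- Cohort 1 children: 7 × (50 × 3 + 50 × 2) = 1,750. Visits: 250 × (9 + 8 + 7 + 6 + 5 + 4 + 3) = 10,500.
- Cohort 3 children: 50 × 8 + 50 × 6 = 700. Visits: 700 × 7 = 4,900.

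All four match the plan. They are the intended counts, before the extensions in SAP Table 2.

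**2. Share of cohort 3 in the pool.** Children: 700 / 2,450 = 28.6%. Visits: 4,900 / 15,400 = 31.8%.

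**3. Weight of cohort 3 in the pooled arm effect.** In a Poisson model with arm and cohort main effects and balanced arms, the pooled log rate ratio is approximately an event-weighted average:

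log RR(pooled) ≈ (1 − w) log RR(cohort 1) + w log RR(cohort 3), with w = 4,900k / (10,500 + 4,900k),

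where k is the frequency of wasting in cohort 3 relative to cohort 1. The documents do not give k, so a range is assumed. The last column takes RR = 1 in cohort 1 and an assumed, selection-driven RR = 0.8 in cohort 3, so the pooled ratio is 0.8^w.

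| k | w | pooled RR |
|---|---|---|
| 1 | 0.318 | 0.93 |
| 1.5 | 0.412 | 0.91 |
| 2 | 0.483 | 0.90 |

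**4. Chance of a significant pooled result when cohort 1 has no effect.** Simulation with 500 runs per row; assumed wasting prevalence 16% in cohort 1 and 24% in cohort 3; village standard deviation 0.25 on the log scale; standard errors clustered by village; two-sided 5%. Overlap is the assumed share of cohort 3 children who share a cohort 1 child's underlying risk.

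| RR in cohort 3 | overlap | cohort 1 alone | pooled |
|---|---|---|---|
| 1.0 | 0 | 4.0% | 3.8% |
| 1.0 | 50% | 4.2% | 4.0% |
| 0.9 | 0 | 3.6% | 7.4% |
| 0.9 | 50% | 5.8% | 8.8% |
| 0.8 | 0 | 5.6% | 21.4% |
| 0.8 | 50% | 6.0% | 19.0% |
| 0.7 | 0 | 5.8% | 40.0% |
| 0.7 | 50% | 6.2% | 39.0% |

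Simulation error near 5% is about √(0.05 × 0.95 / 500) = 1 percentage point. A genuine relapse-prevention effect of the same size would give the same pooled figures, which is why the pooled estimate cannot be attributed to cohort 1.

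**5. Dual membership.** Neither the protocol (3.5.3) nor SAP Table 2 excludes a cohort 1 child who is treated and discharged from entering cohort 3. The extension of cohort 3 inclusion from 2 to 9 months makes this more feasible. If 10%, 30% or 100% of cohort 3 were also in cohort 1, the pool would hold 2,450 − 70 = 2,380, 2,450 − 210 = 2,240 or 2,450 − 700 = 1,750 different children.

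If only the link between a child's two records were ignored, the true standard error would exceed the reported one by a factor of √(1 + 2 × 700 × f × ρ / 2,450), where f is the overlap and ρ the correlation between the two records:
- f = 0.3, ρ = 0.5: √1.086 = 1.04.
- f = 1, ρ = 1: √1.571 = 1.25.

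In the simulation with no shift, village clustering held rejection at 4.0% with 50% overlap. Treating rows as independent gave 17.8% with overlap and 14.4% without, so village clustering matters far more than overlap.

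**The case against.** The strongest reply is that nothing primary depends on this analysis. Each primary outcome belongs to one cohort (SAP 3.4.1) and is modelled there (6.4.1). Section 3.4.2 also makes longitudinal prevalence of wasting a secondary outcome in cohort 3 and incidence of wasting a secondary outcome in cohort 1, so both effects will be available separately in both cohorts. The SAP discloses the selection problem in 3.2, tests for it in 6.2.1 and plans adjusted models in 6.1. All of this stands, and it limits the point to one supplementary figure. It does not repair 6.4.3, which carries over none of the caution. Adjustment can address only measured differences.

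Three stronger readings are tempting, and the documents do not support them.

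- *The pooled estimate is non-randomised.* About 68% of planned visits (10,500 of 15,400) come from the randomised cohort, so it is a mixture.
- *Children are counted twice and the standard errors are too small.* No passage says that any child is in both cohorts. SAP 6.1 describes the samples as distinct, and protocol Table 1 adds them as if separate. A reader might size the overlap from the 37% coverage figure in protocol 3.1.1, but that is a 2015 figure for severe cases, not a probability of treatment for all wasting. The models have a village random intercept (6.1), and clustering by village would absorb most of the problem. What remains open is that 6.4.1 does not name the clustering level and describes the child random intercept in its paragraph on the other longitudinal outcomes, not for the Poisson models.
- *The pooled analysis should be dropped.* That is a preference; labelled properly, it does no harm.

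**Conclusion.** The point holds as a matter of labelling and interpretation of a supplementary analysis. Followed as written, 6.4.3 yields a mixture in which cohort 3 carries about 32% of planned visits, and 32% to 48% of the weight if wasting is one to two times as frequent there. Randomisation does not fully protect that mixture, and a cohort main effect does not restore the protection.

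Under an assumed selection ratio of 0.8, a null cohort 1 effect becomes a pooled ratio of 0.90 to 0.93, significant in 19% to 21% of simulated trials against about 6% for cohort 1 alone. The direction and size of any real selection are unknown; the documents supply no figure, and at a ratio of 0.9 the inflation is slight (7% to 9%). Double counting is possible but not documented, and its effect on standard errors is probably small if errors are clustered by village. The three primary analyses are not affected.

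**What to change.** Amend SAP section 6.4.3 by a dated note, or apply the same rules in the report if the analysis has already been run:

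- Call the pooled analysis exploratory, and name cohort 1 alone as the randomised estimate for longitudinal prevalence and for incidence of wasting.
- Add an arm-by-cohort interaction, and print the two cohort-specific effects, already planned in 3.4.1 and 3.4.2, beside the pooled one.
- Repeat the caution of section 3.2, and say that pooled incidence combines wasting in community children with relapse.
- Link children by one identifier across cohorts, report how many are in both, and let each child-month enter once.
- State that robust standard errors in the pooled models are clustered by village.

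The cost is a few sentences, one data check and less apparent precision in a supplementary analysis. Timing matters for the check: SAP section 4 has identifying data destroyed once collection and validation are complete, so after that the match must rest on study codes. The consented linkage of treatment records to cohort 1 and 3 data in protocol 3.5.3 may provide a route.
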